Our study will implement the caregiver survey and the medical record abstraction tools in the PFK ABD population. Caregivers of all 8,080 newly enrolled ABD children will be invited to participate in the survey. We estimate that our methods will yield 2,750 caregiver survey respondents. The estimated 34% response rate considers a combination of those who are unreachable based on available contact information and those who are reached but who opt out of participation. This sample size will allow us to estimate performance on each survey-based care coordination indicator within a 95% confidence interval of ± 1.5 percentage points (conservatively assuming underlying performance of 50%). Confidence interval widths for age, gender, and urban/rural subpopulations will range from ± 1.8 to ± 3.7 . This sample size will allow us to identify a significant urban/rural difference ($\alpha=0.05$) of 0.05 percentage points (i.e., 0.50 vs. 0.55) with a power of 0.83.

Medical Record Abstraction

Participants & Sample Size

We further estimate that 1,000 of those who complete the survey will consent to a review of their medical records that will allow data collection on medical record review based measures that can be linked to survey data and ultimately medical claims data. This consent rate is based on experience in current pilot work. This sample size will allow us to estimate performance on each medical record-based care coordination indicator within a 95% confidence interval of ± 2.9 percentage points (conservatively assuming underlying performance of 50%). Confidence interval widths for age, gender, and urban/rural subpopulations will range from ± 3.6 to 7.0. This sample size will allow us to identify a significant urban/rural difference ($\alpha=0.05$) of 0.10 percentage points (i.e., 0.50 vs. 0.60) with a power of 0.89.

Analysis

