The underlying population for this study is all children up to age 18 enrolled in the Partners for Kids (PFK) on May 30th 2015 who had been previously enrolled in fee-for-service (FFS) Medicaid and transitioned into PFK as a result of the ABD policy change. The primary analytic data comes from Ohio Medicaid administrative claims. Claims data have different missing data issues than do other primary or even secondary data sets on several dimensions. First, many of the fields are mandatory, which means fields such as procedure code and Medicaid eligibility status will

be 100% complete. Second, although claims data have the traditional limitations of any administrative data, including the lack of information of services paid fully out-of-pocket or financed through Medicare, only services provided through Medicaid will be used in the analysis, which will take a Medicaid/agency perspective. This means that services and expenditures will not aim to be a complete record, but those covered through the Medicaid program. We will clearly indicate the scope of analysis in publications. For the subsets of claims data merged with survey and medical records, we do not anticipate missing data problems for the same reasons above.

The estimated size of this population is 8,000. Because of the qualitative nature of Aim 1 we do not propose a missing data plan. The following assumptions have been made regarding rates of participation from this population for Aims 2 and 3:

Aim 2 – Caregiver Survey

We expect 34% percent of the eligible caregivers to complete the caregiver survey. This is based on assumptions from previous studies with this population regarding degree of incorrect addresses for the opt-out mailing, opt outs, missing/non-functional telephone numbers, and refusal when contacted.

- *Prevention of missingness*– We will use alternative sources of contact information (e.g. EHR records, internet look-up sites) for those families with missing telephone numbers.
- *Monitoring of missingness* – we will record and report the following statistics: % of invitation letters returned by the post office, % opting out, % bad telephone numbers that cannot be found after research, and % refusal by reached families. For each of these percentages, we will describe the lost respondents by gender, age, urban/rural residence, and diagnosis category using PFK data (note: race is not reliably available on the PFK data).

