We expect 35% percent of those completing the telephone survey to consent to medical record abstraction.

- *Prevention of missingness* – The script requesting medical record access will clearly explain the reason for access and the processes for maintaining confidentiality.
- *Monitoring of missingness*– We will describe the lost respondents by gender, age, urban/rural residence, and diagnosis category using claims data. We will also test the relationship between perceptions of care coordination and consent to medical record abstraction using data from the telephone survey.

A consort-style diagram will be used to illustrate potential participant loss or refusal at each stage of the study **(MD-4)**.

Aim 3 – Utilization Analysis

Over 95% of the population will be included in claims data analysis looking at overall pre-/post-policy change utilization analysis. The primary risk of missingness for this analysis is failure of successful linking between the FFS (pre) and PFK (post) data. After acquisition of the data, we will first assess the data quality. Like the traditional Medicaid plan, PFK reimburses physicians

on the basis of services provided (fee-for-service), therefore we expect that the payment data and other fields such as patient id, date of service, and procedure codes required for reimbursement will be populated for each claim billed to Medicaid/PFK. The demographic files (e.g. gender, race) may also have missing data, which is anticipated to be proportionally small, based on the team's prior experience with claims.

- Prevention of missingness – We will investigate each non-match. When there is no matching Medicaid ID across the two databases, we will directly check the record to identify potential transposition or typographical errors. If no such error can be found, we will attempt to use probability matching using date of birth, zip code of residence, gender, and soundex last name to link records.
- Monitoring of missingness– We will calculate and report the final “no-match” rate between PFK and state FFS data.

Statistical methods and sensitivity analysis to handle missing data (MD2, MD3, MD5)

Aim 2 – Caregiver Survey

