- The ACO (PFK) mails letters to potentially eligible enrollees describing the study and offering them the option of opting out of the sampling frame. Contact information for those who do not opt out will be sent to CSRL for survey contact.
- CSRL will send letters to all non-opt out families. The letter will include thanks for willingness to participate, telephone survey logistics, and a web address that can be used to complete the survey on their own. We expect up to five percent of respondents to use the web-based survey.
- Trained interviewers will make up to 10 telephone attempts for each caregiver who does not complete the online survey. When telephone numbers are found to be non-functional, research staff will make reasonable efforts to find working numbers through use of Lexus-Nexus and through working with PFK staff with access to electronic medical record (EMR) information that may offer updated contact information.
- Surveys will be conducted using a computer-assisted telephone interviewing (CATI) system with interviewer performance monitored through review of randomly selected taped interviews.
- Prior to the close of the interview, the interviewer will request verbal consent for a review of care coordination documentation in their medical records and for linking of their survey responses to medical record and claims data.
- All individuals who complete the interview will be mailed a \$20 gift card in appreciation of their participation.

Key Decisions

- We will keep the survey wording the same because it has been field tested and underwent cognitive development testing.
 - It is not necessary to allow for N/A (for e.g. 5E – needing equipment, in all the piloted work this was never an issue).
 - Refusals or don't know – they may not be read, but interviewer can fill it in. If subject says they don't know, record in notes and leave unanswered or say respondent refused. For programming purposes, refuse/don't know is a (non-read) option. Email-based surveys can allow blanks (in fact are mandated to allow).
- Web survey
 - We will pilot the web survey.
 - CSRL will do in-house.
 - We will also pilot with Patient Advisory Panel prior to April 6th patient advisory panel meeting.
 - We will work on web survey first to make sure it is available for pilot testing, and then focus on the phone survey.

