Based on our pilot work, we expect that 1,000 caregivers who complete the phone survey will also provide consent for abstraction of their medical records for MR based care coordination measures. Data for Medical record-based care coordination measures will be collected primarily through review of the Epic EMR at Nationwide Children’s Hospital (NCH) conducted by an experienced, trained NCH abstractor using a field-tested data abstraction tool. The integrated EMR at NCH allows review of NCH inpatient visits and primary and specialty care services provided by physicians in the NCH system. We estimate 50% of ABD children enrolled in PFK were seen in the NCH system in the past year. If a participant lists a main provider outside of the NCH system, a copy of the relevant medical records will be requested from that provider for review. The first 20 records will be re-reviewed by a second abstractor for quality control and training.

Aim 3

Assumptions

- PFK data and claims data are housed on servers at NCH.

- NCH has permission from PFK to use data.
- NCH has permission from the state to use data.
- NCH will provide a limited de-identified dataset at the person-month level.
- Data will be provided in SAS and STATA format.
- Data will be available for download from a secure server using a double-password system.
- [name], [name], [name], [name], and the NCH programmer will have access to the data.

Steps for Data Preparation and Access

1. [name] and [name] will develop a programming guide for the programmer.
2. NCH Programmer links PFK and state data (EHR data, claims data) to study data (caregiver data) and strips identifiers.
3. NCH Programmer creates an analytic file.
4. NCH Programmer runs frequencies.
5. NCH Programmer makes de-identified dataset available in both SAS and Stata formats.
6. NCH will notify team that data are available for download.
7. [name] will log on to server using double-password system (VPN-like system).
8. [name] will download and house data on secure site at UNC & OSU.

Dissemination Plan

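### The record-review precision (±2.9) and power (0.89) rest on 1,000 abstracted charts, but the plan's 35% consent rate gives about 963 consents (914 at the lowest), and no allowance is made for outside charts that are not returned

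*Combined protocol and SAP*

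**What the plan says.** **Survey yield.** Under Aim 2, Caregiver Survey, Participants & Sample Size: "Caregivers of all 8,080 newly enrolled ABD children will be invited to participate in the survey", and "We estimate that our methods will yield 2,750 caregiver survey respondents".

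**Consents.** Under Medical Record Abstraction in the same aim: "We further estimate that 1,000 of those who complete the survey will consent to a review of their medical records". The rate is attributed to pilot work. From this number the plan derives a 95% interval of ±2.9 points at 50% performance, subgroup intervals of ±3.6 to 7.0, and power 0.89 for 0.50 vs 0.60 between urban and rural children. The Medical Record Review part of Procedures repeats 1,000 and describes these caregivers as completing the phone survey.

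**Consent rate.** In Handling Missing Data, Aim 2: "We expect 35% percent of those completing the telephone survey to consent to medical record abstraction".

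**Survey mode.** In Caregiver Survey Methodology, the interviewer asks for record consent before the call closes, and the plan adds: "We expect up to five percent of respondents to use the web-based survey".

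**Chart source.** In Medical Record Review: "We estimate 50% of ABD children enrolled in PFK were seen in the NCH system in the past year". If the caregiver names a main provider outside that system, "a copy of the relevant medical records will be requested from that provider for review". No return rate appears anywhere.

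**The concern.** Two steps lie between a completed survey and a scored record-based indicator: consent, and possession of the chart. At the first, the sizing uses a count that the plan's own rate does not give. At the second, the sizing makes no deduction, although the plan describes a retrieval route that can fail.

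What is at stake is how the record-based results are read. One declared purpose of Aim 2 is to judge whether care coordination is consistent across subpopulations. A reader who sees no significant urban/rural difference would weigh it against the stated power of 0.89, and would read each indicator against ±2.9. Both should belong to the number of charts that the plan expects to abstract.

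**Working it through.** **Inputs from the documents.** 2,750 respondents; 8,080 invited ("The estimated size of this population is 8,000" is the alternative figure, in the missing-data section); consent 35% of telephone completers; web share up to 5%; indicator performance 0.50; alpha 0.05. Sidedness, urban/rural split and use of a finite population correction are not stated.

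**1. Reproduce the stated half-width.** Half-width = 1.96 × √(0.25/n), multiplied by √((N−n)/(N−1)) if corrected.
- n = 1,000, uncorrected: 3.10.
- n = 1,000, corrected with N = 8,080: 2.90. With N = 8,000 it is also 2.90.
- Cross-check on the survey, n = 2,750, corrected: 1.52, matching the stated ±1.5.

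So ±2.9 is the corrected value at 1,000, with nothing deducted between consent and chart.

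**2. Reproduce the stated power.** Normal approximation for two proportions, 0.50 vs 0.60, two-sided 0.05, 500 per group, no correction: 0.890. The stated 0.89 is matched. The same model for the survey (2,750; 0.50 vs 0.55) gives 0.75, while the plan states 0.83. The model therefore fits one of the two power figures and is an inference.

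**3. Consents from the plan's rate.**
- 0.35 × 2,750 = 962.5, about 963.
- 0.35 × 0.95 × 2,750 = 914.4, about 914, if the maximum web share is removed and no web completer is asked.
- Rate needed for 1,000: 1,000/2,750 = 36.4%, or 1,000/2,612.5 = 38.3%.

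**4. Effect of the consent mismatch alone.**

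| Charts | Half-width, corrected | Power, two-sided, equal split, uncorrected |
|---|---|---|
| 1,000 | ±2.90 | 0.890 |
| 963 | ±2.96 | 0.878 |
| 914 | ±3.05 | 0.861 |

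The change is 0.06 to 0.15 points of half-width and about 1 to 3 points of power.

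**5. Chart return (illustration only).** Assume that half of the consenting children have their chart outside NCH. The documents give no such figure; the 50% in Medical Record Review is only a proxy. Charts = consents × (0.5 + 0.5 × return rate). Power is from the same model as in step 4.

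| Assumed return of outside charts | From 963 consents | From 914 consents |
|---|---|---|
| 100% | 963; ±2.96; 0.88 | 914; ±3.05; 0.86 |
| 75% | 843; ±3.20; 0.83 | 800; ±3.29; 0.81 |
| 50% | 722; ±3.48; 0.77 | 686; ±3.58; 0.75 |

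These rows show how sensitive the figures are. They do not estimate what will happen.

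**The case against.** **The firm discrepancy is small.** Both places that give 1,000 call it an estimate or expectation and cite pilot work, and 36.4% against 35% could be rounding. This stands as to size. It does not remove the inconsistency, because the precision and power are printed at 1,000.

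**914 is the worst case.** It takes the maximum web share and assumes that no web completer can consent. The sizing paragraph counts survey completers without a mode limit, and the survey decisions mention an agree/do-not-agree box at the end of the survey, though as a record of the interviewer's verbal consent. The missing-data and record-review sections do say telephone or phone. So 963 is the plain reading and 914 a possible lower end.

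**Large power losses are not shown.** A reader might infer that, with half the charts outside NCH, power drops to 0.75 or lower. The documents do not support that. The 50% describes all enrolled children seen at NCH in the past year, whereas the outside request depends on the main provider that a consenting caregiver lists. No return rate is given at all.

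**The power model is not known to be the plan's.** With the finite population correction applied to power as well, an equal split gives 0.925 at 1,000 and 0.898 at 914, neither below 0.89. A 70/30 split with the correction gives 0.88 for records and 0.84 for the survey, close to both stated values. So it cannot be said that the analysis lacks 0.89 power under every reasonable method. This stands, and is itself a reason to state the method.

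**Part is already handled.** Aim 2 specifies available-case analysis, and a consort-style diagram is planned for loss at each stage. The record indicators are also mainly descriptive, and Aim 3's primary data are claims. This stands, and it lowers the priority.

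**Conclusion.** The point holds as a minor inconsistency. The record review is sized on 1,000 consents, while the plan's only printed rate gives about 963, or 914 on the narrowest reading. With the finite population correction that reproduces ±2.9, the half-width becomes about ±3.0 to ±3.05. Power falls by about 1 to 3 points, from 0.89 to 0.88 or 0.86, under the inferred two-sided, equal-split, uncorrected model.

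In addition, the sizing equates consents with abstracted charts and makes no allowance for outside charts that are requested and not returned. That is an omission whose size cannot be derived from the documents. It could exceed the consent effect or be negligible. A conclusion that the record review is seriously underpowered would go beyond what the plan shows.

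**What to change.** - Reconcile 1,000 with 35% across the Aim 2 sizing paragraph, the missing-data section and Medical Record Review, and say whether web completers are asked for record consent.
- Restate ±2.9, the ±3.6 to 7.0 subgroup range and the 0.89 at the expected number of abstracted charts: consents × (share held at NCH + outside share × return rate).
- State the urban/rural split, the sidedness, and whether the finite population correction is used for intervals and for power.
- Use the pilot chart-return rate if there is one. Otherwise show, for example, 50%, 75% and 100% return of outside charts, labelled as assumptions.
- As an optional refinement, count consented children whose chart was not obtained as a stage in the planned flow diagram.

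The cost is a recalculation and some wording, with no extra participants. The downside is that the stated precision and power will look slightly less favourable.

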Administrative data-derived measures include items such as continuity of care, use of the emergency department, hospitalizations, and access to primary and specialty care, timely follow-up after initial prescriptions of ADHD medications or after psychiatric hospitalization.[45,46] We will incorporate recent methodological advances in operationalizing these measures from administrative data.[47] All study measures will be reviewed with our Patient Advisory Panel in order to prioritize the measures determined to be of greatest importance to our patient population. The Patient Advisory Panel may also propose and prioritize additional patient-centered outcome measures during the first two years of the project.

Key treatment variable: The key variable of interest is the enrollment in the ACO by children with disabilities. This “treatment” was assigned to children seen by one of the health care facilities within PFK’s 34-county service area in Ohio beginning in July 2013. Data from PFK-enrolled children prior to enrollment (July 2010 – June 2013) will serve as primary controls, adjusting for age and length of time on Medicaid. Children who were enrolled in Ohio Medicaid with ABD eligibility in other areas of the state will serve as additional potential controls using Medicaid claims data. We cannot use these children as primary controls due to important limitations in the data, namely the inability to attribute children to other ACOs outside the 34 county PFK region. PFK’s unique arrangement with the state allows us to clearly identify the ACO catchment area by county and thus we can clearly attribute these patients to PFK.

Patient Characteristics: Our analysis is conducted on a diverse population of children and adolescents. Their characteristics vary by age, gender, race, Latino ethnicity, SSI status, county of residence, diagnoses, procedures received, length of time on Medicaid and other patient characteristics as detailed in **Appendix F**. We will create baseline disease adjustment categories using the Chronic Illness and Disability Payment System, which was specifically designed for disabled Medicaid enrollees. [48]

Methods: Following the latest guidance on PCOR methods from the PCORI Methodology Report, we will define the analysis sample that represents the distribution of demographic and conditions among ABD children in Ohio from histories available in the administrative data.[49] We will use approaches appropriate to PCOR including mixed qualitative and quantitative methodologies in a quasi-experimental study design for this Aim.

Quantitative Analysis: Using the interrupted time series analysis for statistical models, we will estimate the effect of switching from FFS to ACO while controlling for secular trends. This method examines both the change in the average level of each outcome in the post period as

compared to the pre-ACO period, as well as changes in the trends in each outcome. For example, an interrupted time series analysis can determine whether access to outpatient visits with specialists increases or decreases after the children are enrolled in PFK as well as whether changes in the rate of access over time are greater or lower as compared with the pre-ACO period. Outcome models will be run separately on each outcome using generalized estimating equations with appropriate distributional assumptions for each type of outcome variable (e.g., binary, continuous). The key variables will be an indicator of the ACO enrollment period and its interaction with time trends.

While we believe this is the strongest study design for this Aim given the available data, the lack of a control group cannot rule out other explanations for differences in outcomes over time. Therefore, we will carefully consider alternative explanations to other trends with our Patient Advisory Panel and other key experts once we obtain preliminary analytic results. We will additionally examine the potential for controls from children in other regions of Ohio for a case/control analyses. Although ACO assignment was mandatory and assigned based only on region and thus may not suffer from self-selection bias, if we are able to incorporate data from children in other regions, we will carefully examine the baseline characteristics, utilization during the pre-treatment period and risk factors between ACO and other ABD children in Ohio to ensure balance in covariates. Incorporating control data from Medicaid claims for children in states other than Ohio is not plausible, given that these data are available with a three-year lag and thus post-period analysis would not be possible during our study period.

Sub-group analysis: Although our primary goal is to estimate the effect of ACO enrollment on vulnerable ABD children overall, we will also estimate the *heterogeneity of the ACO treatment effect* in populations defined by age, race/ethnicity, gender, care coordination metrics and diagnostic group to the extent allowable by sample size. The specific subgroups will be identified in advance collaboratively with our stakeholders. This sub-analysis will control for the health status and disease progress of a patient during the 6-year period.

We will also look at the impact of specific elements of care coordination provided on a subgroup of our population using information collected in our caregiver survey and medical record review. For example, as noted above, one of our potential outcomes variables is use of the emergency department. One potential research question is whether emergency department use is lower in children whose caregivers reported receipt of an understandable visit summary after their last outpatient visit.

Data Safety, Monitoring, and Handling

Aim 1

Interview data collected from participants will be identified only by an assigned participant ID number, not by name. The data confidentiality and informed consent process will be explained by the investigator prior to the start of the interview and before the recording begins.

Participants will have the option to not respond to any question and to not have their interviews recorded.

Similarly, for focus groups, participants will be identified only by number, not by name. The data confidentiality and informed consent process will be explained by the moderator prior to the start of the discussion, and before the recording begins. Participants will have the option to not respond to any question posed; if they do not wish to be recorded, they may elect to leave the discussion group.

Digital recordings and transcriptions of interview and focus group sessions, and any documents collected from ACO stakeholders will remain in the possession of the study investigators at all times and will be reviewed in seclusion. These will all be secured in a locked office at all times and stored on a password-protected computer. Upon completion of the study, all electronic and hard copy data will remain in password-protected files and reside with the principal investigator; these will be destroyed after five years.

Any forms and incentive receipt lists, which include patient names and study ID numbers, will be stored in locked file cabinets in a locked file room in a secure building

For both focus groups and interviews, participants' comments will never be quoted or reported in ways that disclose their identities. For medical record and Medicaid claims data, findings will only be reported in aggregate or summary form.

Aim 2

Data from the telephone survey will be entered into an electronic database as it is collected. Once surveying is complete, a formatted and labeled SAS data file will be provided to the PI using a HIPAA compliant data transfer protocol. The data from the medical record abstraction will be directly entered into a Redcap database, which will also export data into a SAS format. Ultimately, linked survey, medical records, and claims data will be housed on a secured server at Nationwide Children's Hospital. Access to the data on the server will be limited to the project's investigators and programmer.

Aim 3

NCH will provide UNC with de-identified data from the FECC survey, medical records, and medical claims.

Handling Missing Data – PCORI Methodology Standards MD-1-5

Describe methods to prevent and monitor missing data (MD-1)

The underlying population for this study is all children up to age 18 enrolled in the Partners for Kids (PFK) on May 30th 2015 who had been previously enrolled in fee-for-service (FFS) Medicaid and transitioned into PFK as a result of the ABD policy change. The primary analytic data comes from Ohio Medicaid administrative claims. Claims data have different missing data issues than do other primary or even secondary data sets on several dimensions. First, many of the fields are mandatory, which means fields such as procedure code and Medicaid eligibility status will

be 100% complete. Second, although claims data have the traditional limitations of any administrative data, including the lack of information of services paid fully out-of-pocket or financed through Medicare, only services provided through Medicaid will be used in the analysis, which will take a Medicaid/agency perspective. This means that services and expenditures will not aim to be a complete record, but those covered through the Medicaid program. We will clearly indicate the scope of analysis in publications. For the subsets of claims data merged with survey and medical records, we do not anticipate missing data problems for the same reasons above.

The estimated size of this population is 8,000. Because of the qualitative nature of Aim 1 we do not propose a missing data plan. The following assumptions have been made regarding rates of participation from this population for Aims 2 and 3:

Aim 2 – Caregiver Survey

We expect 34% percent of the eligible caregivers to complete the caregiver survey. This is based on assumptions from previous studies with this population regarding degree of incorrect addresses for the opt-out mailing, opt outs, missing/non-functional telephone numbers, and refusal when contacted.

- *Prevention of missingness*– We will use alternative sources of contact information (e.g. EHR records, internet look-up sites) for those families with missing telephone numbers.
- *Monitoring of missingness* – we will record and report the following statistics: % of invitation letters returned by the post office, % opting out, % bad telephone numbers that cannot be found after research, and % refusal by reached families. For each of these percentages, we will describe the lost respondents by gender, age, urban/rural residence, and diagnosis category using PFK data (note: race is not reliably available on the PFK data).

We expect 35% percent of those completing the telephone survey to consent to medical record abstraction.

- *Prevention of missingness* – The script requesting medical record access will clearly explain the reason for access and the processes for maintaining confidentiality.
- *Monitoring of missingness*– We will describe the lost respondents by gender, age, urban/rural residence, and diagnosis category using claims data. We will also test the relationship between perceptions of care coordination and consent to medical record abstraction using data from the telephone survey.

A consort-style diagram will be used to illustrate potential participant loss or refusal at each stage of the study **(MD-4)**.

Aim 3 – Utilization Analysis

Over 95% of the population will be included in claims data analysis looking at overall pre-/post-policy change utilization analysis. The primary risk of missingness for this analysis is failure of successful linking between the FFS (pre) and PFK (post) data. After acquisition of the data, we will first assess the data quality. Like the traditional Medicaid plan, PFK reimburses physicians

on the basis of services provided (fee-for-service), therefore we expect that the payment data and other fields such as patient id, date of service, and procedure codes required for reimbursement will be populated for each claim billed to Medicaid/PFK. The demographic files (e.g. gender, race) may also have missing data, which is anticipated to be proportionally small, based on the team's prior experience with claims.

- Prevention of missingness – We will investigate each non-match. When there is no matching Medicaid ID across the two databases, we will directly check the record to identify potential transposition or typographical errors. If no such error can be found, we will attempt to use probability matching using date of birth, zip code of residence, gender, and soundex last name to link records.
- Monitoring of missingness– We will calculate and report the final “no-match” rate between PFK and state FFS data.

Statistical methods and sensitivity analysis to handle missing data (MD2, MD3, MD5)

Aim 2 – Caregiver Survey

Methods for statistical handling of missing responses on the Family Experiences of Care Coordination survey are documented in the survey's scoring guide. We will use these methods to assure that our results are consistent with those being generated in other implementations of the survey. Missing data will not be imputed, however, we will use sensitivity analysis to estimate the effect of differential non-response by age, gender, urban/rural residence, and diagnosis category. We do not hypothesize differential missingness.

Aim 3 - Utilization Analysis

The pre-/post-policy change utilization analysis will be performed on all individuals where we are able to link FFS and PFK claims. We expect a low non-link rate. However, to estimate the impact of the missing data, we will conduct sensitivity analysis by testing change in setting-specific utilization if all the unlinked cases were at the 90th percentile of their age/gender/diagnosis category group and if all unlinked cases were at the 10th percentile of their age/gender/diagnosis category group.

For time invariant missing variables in the FFS or PFK data, such as gender or race, we will carry the last observation forward, assuming gender and race is unchanged for each individual. In the rare case of substantial amount of other types of missing data in the claims, we will employ Multiple Imputation (MI) methods to generate imputations for the missing values, from predicted probabilities estimated based on the complete data (observed and missing data).

Procedures

Aim 1

In all aspects of Aim 1, we will use purposive sampling, attempting to get a mix of participants and to maximize the diversity of our sample in terms of perspectives that we expect to be

relevant to the coordination of care for children with disabilities. For interviews with ACO stakeholders, we will sample purposively from four groups: ACO leaders, care coordinators, clinicians, and payor representatives. Each group will provide a different perspective on coordination objectives and strategies. For focus groups with youths and caregivers and interviews with caregivers, we will sample based on broad categories of condition and geographic location (rural v. urban). This approach will allow us to maximize the overall variation in our sample through inter-group diversity, while simultaneously ensuring focused, productive discussions within each group through intra-group similarity. Finally, for the interviews with Caregivers, we intend to select 30 parents, as this number provides a large enough sample to gather a rich mix of different stories and experiences in rural and urban settings and from parents of children with different types of disabilities.

To be eligible to participate in ACO stakeholder interviews, participants must be involved with the ACO as either an ACO leader, a care coordinator or clinician, or as a representative of a payor organization (i.e., insurer). To be eligible to participate in focus groups or caregiver interviews, the child (as the participant or of the caregiver) must:

1. have resided continuously in the region served by the ACO, have been continuously enrolled in Medicaid, and have had ABD status (i.e., Medicaid disability status) since at least one year before the policy change;
2. be no more than 18 years of age at the time of data collection; and
3. have been, at the time of the policy change, at least 14 years of age for youth focus groups or 2 years of age for caregiver focus groups and interviews.

Children under the age of 15 will be excluded on the grounds that they may not be able to recall with sufficient detail their experiences under the previous Fee-for-service system. These criteria ensure that participants will have had sufficient, relevant experience under both systems to be able to compare them.

Our recruitment strategies vary by sub-aim. For sub-aim 1a (Interviews with ACO Stakeholders) we will work with the ACO to identify and select key informants from each of the four stakeholder groups based on their knowledge about and experience with care coordination related decisions and practices for ABD children. Research staff already have relationships with key leaders at the Partners For Kids ACO. Researchers will use these individuals both as participants and also to identify other key stakeholders within the Partners For Kids organization and at the payor organizations with which Partners For Kids deals. The researchers will send information about the study along with an invitation to participate to these individuals via email. ACO stakeholders will not be compensated for participation.

For sub-aim 1b (Focus groups with youths and caregivers and interviews with caregivers) we will recruit participants through the following means:

1. distribution of flyers throughout ACO provider sites and by ACO care coordinators who will distribute flyers to all of their patients/caregivers with whom they interact during the study period;
2. recruitment email sent through Voice's For Ohio's Children listserv; and

3. snowball-sampling approaches to identify additional participants based on referrals from other participants.

Caregivers and patients (i.e., youths) who participate in focus groups will receive a \$50 gift card and light meal for participation. Caregivers who participate in interviews will receive a \$50 gift card. Compensation will not be pro-rated. If participants choose to discontinue participation once the interview or focus group has started, they will still be compensated the full amount.

